## 2 Trial Objectives

### 2.1 Primary Objectives

#### *Tdap immunogenicity*

- To demonstrate the non-inferiority of the humoral immune response to the Tdap booster dose concomitantly administered with the first dose of CYD dengue vaccine as compared to sequential administration, measured 28 days after Tdap booster dose

#### *CYD dengue vaccine immunogenicity*

- To demonstrate the non-inferiority of the humoral immune response to the first dose of CYD dengue vaccine concomitantly administered with Tdap as compared to sequential administration, measured 28 days after the first dose of CYD dengue vaccine

The endpoints for the primary objective(s) are presented in [Section 9.1](#).

### 2.2 Secondary Objectives

#### *CYD dengue vaccine Immunogenicity:*

- To demonstrate the non-inferiority of the humoral immune response of 3 doses of CYD dengue vaccine with the first dose concomitantly administered with Tdap as compared to sequential administration, measured 28 days after the third dose of CYD dengue vaccine
- To describe the humoral immune response at baseline and 28 days after the first and third doses of CYD dengue vaccine, in each and any group

#### *Tdap Immunogenicity:*

- To describe the humoral immune response of Tdap vaccine at baseline and 28 days after concomitant administration with the first dose of CYD dengue vaccine as compared to the sequential administration, in each and any group

#### *Safety*

- To describe the safety of the CYD dengue vaccine and of the Tdap booster dose after each and any injection in each group

The endpoints for the secondary objective(s) are presented in [Section 9.2](#).

## 3 Investigators and Trial Organization

This trial will be conducted in approximately 4 centers in the Philippines. The Principal Investigators and any sub-Investigators at the individual sites will be coordinated by one Coordinating Investigator. Details of the trial centers, the Investigators at each center, and the Coordinating Investigator(s) are provided in the “List of Investigators and Centers Involved in the Trial” document.

#### *Independent Data Monitoring Committee*

An Independent Data Monitoring Committee (IDMC) will be involved in the regular review of hospitalized VCD cases, including assessment of severity. Additionally, any related serious adverse event (SAE) or death will be promptly reviewed by the IDMC.

### ***Safety Management Team***

An internal safety management team (SMT) will perform a safety analysis on safety data during the conduct of the trial.

### ***Laboratories***

Immunogenicity assessments will be performed by Sanofi Pasteur Global Clinical Immunology (GCI) (Swiftwater, Pennsylvania, USA) or outsourced laboratory under the management of GCI.

## **4 Independent Ethics Committee/Institutional Review Board**

Before the investigational product can be shipped to the investigational site and before the inclusion of the first subject, this protocol, the informed consent form(s) (ICF) and assent form (AF), subject recruitment procedures, and any other written information to be provided to subjects must be approved by, and/or receive favorable opinion from, the appropriate Independent Ethics Committee (IEC) or Institutional Review Board (IRB).

In accordance with Good Clinical Practice (GCP) and local regulations, each Investigator and/or the Sponsor are responsible for obtaining this approval and/or favorable opinion before the start of the trial. If the protocol is subsequently amended, approval must be re-obtained for each substantial amendment. Copies of these approvals, along with information on the type, version number, and date of document, and the date of approval, must be forwarded by the Investigator to the Sponsor together with the composition of the IEC/IRB (the names and qualifications of the members attending and voting at the meetings).

The Investigator will submit written summaries of the status of the trial to the IEC/IRB annually, or more frequently if requested. All SAEs occurring during the trial that are related to vaccination will be reported by the Investigator to the IEC/IRB, according to the IEC/IRB policy.

## **5 Investigational Plan**

### **5.1 Description of the Overall Trial Design and Plan**

#### **5.1.1 Trial Design**

This is a Phase IIIb, randomized, open label, multicenter study in 688 healthy subjects aged 9 to 60 years in the Philippines.

Subjects received the first dose of the CYD dengue vaccine either concomitantly or sequentially with a booster dose of Tdap vaccine (Adacel®)

Subjects were randomized according to a 1:1 ratio into one of the 2 following groups with stratification on age (9 to 11 years, 12 to 17 years, 18 to 45 years and 46 to 60 years):

- **Group 1:** subjects were administered the first dose of CYD dengue vaccine concomitantly with the booster dose of Tdap vaccine at the second visit (V02; M1)
- **Group 2:** subjects were administered Tdap vaccine at the first visit (V01; D0), and then CYD dengue vaccine 28 days later at the second visit (V02; M1)

The stratification will be considered in order to balance the potential difference in terms of booster response by age group for the pertussis antigens (PT, FHA, PRN and FIM2+3).

Since the CYD dengue is administered according to a 3-dose schedule, given 6 months apart, initial trial design included administration of the second and third doses of CYD dengue vaccine at V04 (Month 7 [M7] and at V06 (M13) in all subjects.

All but 19 subjects (from both, Group1 and Group 2) did receive dose 2 of the CYD dengue vaccine as planned. However, as per changes in the conduct of the study reflected in this Protocol Amendment 1 (see also [Section 1.4](#)), the following will be applied:

- All vaccinated subjects will be informed about their baseline dengue serostatus and what it means as soon as possible
- All subjects will be asked about their willingness to continue participating in this study, and consent will be formalized by signing an ICF and/or AF addendum, as applicable.
- Subjects seropositive at baseline will additionally be asked for consent to receive remaining CYD dengue doses.
- Subjects seronegative at baseline will be able to continue in the study for safety follow-up if they consent to, but will not receive further injections of CYD dengue vaccine.
- Subjects seronegative at baseline who were vaccinated during this study will have timely access to appropriate care in the event of suspected dengue, for 10 years from the date of last dengue vaccination.

Time between communication of the results from the exploratory analyses and approval of Protocol Amendment 1 by the competent authorities and for the associated logistic tasks will result into a hold of study activities of several months (approximately 4-6 months). Study-hold intervenes after V03, V04 or V05, depending on each subject's visit-calendar at the time of study-hold.

Blood samples collected before dose 1 of the vaccine (at V01 for Group 2 and at V02 for Group 1) will be used to determine dengue serostatus at baseline. Dengue serostatus will be determined using the Dengue PRNT. A “seropositive” subject has been generally defined by a PRNT titer  $\geq 1:10$  to any dengue serotype at baseline, and a “seronegative” subject has been defined by a PRNT titer  $<10$  for all four dengue serotypes. Only subjects identified as dengue seropositive will be eligible to receive further vaccine injections.

In order to communicate to each subject his/her dengue serostatus at baseline, there will be either 1 unscheduled visit and /or phone call during the study-hold, before the next visit initially planned (at V06 at the latest):

The subject will consent to continue participation in the study by signing an ICF/AF addendum 1 at subject's next planned visit (either V04, V05 or V06).

Thus, dose 2 and 3, or dose 3 only (provided that dose 2 was received, as planned) will be administered only to those subjects dengue seropositive at baseline who consent continue participation in the study and consent receiving the remaining CYD dengue doses planned.

A 6 months safety follow up is planned for all subjects who received at least 1 dose and who consent to continue participation in the study. This period will start after the last CYD dose the subject received (whether 1, 2 or 3 doses).

At the time vaccinations were paused, subjects had already provided 2 to 3 blood samples (BL), depending on the allocation group. Only dengue-exposed subjects who will continue in the study and choose to receive remaining CYD dengue doses will provide 1 subsequent BL, as initially planned in Protocol Version 1.0.

Additional blood samples might be collected in case of SAEs (including AEs of special interest [AESIs]) and to assess AEs that may be indicative of viscerotropic or neurotropic disease (see Guidelines for Assessing Viscerotropic and Neurotropic AE).

In case of hospitalized suspected dengue case, one unplanned BL (= acute BL) will have to be collected within the first 5 days after fever onset for virological confirmation of dengue disease. (If this cannot be accomplished, this sample should still be obtained as soon as possible thereafter, for IDMC severity assessment).

All female subjects of childbearing potential will provide urine samples for urine pregnancy test before each injection.

Immunogenicity of the Tdap booster dose will be evaluated before and 28 days after injection in both groups. Immunogenicity of the CYD dengue vaccine will be evaluated before the first injection and 28 days after the first and the third injections in both groups. The safety of the two vaccines will be assessed after each injection in both groups.

For seropositive subjects who consent continue participation in the study and administration of remaining CYD dengue doses, due to period of study-hold, the duration of each subject's participation in the trial will be approximately 23-25 months, since it will be extended by 4-6 months with respect to the initial plan (ie, as per protocol version1.0: approximately 19 months, including a vaccination phase of 12 months for subjects in Group 1 and 13 months for subjects in Group 2, followed by a safety follow-up period of 6 months after the third injection of CYD dengue vaccine).

For seropositive subjects who consent continue participation in the study but refuse to receive remaining CYD dengue doses and seronegative subjects who provide their consent to continue participation in the study, their participation in the trial will be less than 19 months as initially planned. (i. e., taking into account the study-hold and the 6 months safety follow up

Subjects declining continue participation in the study will end the study on the date this decision is communicated to the Sponsor.

### 5.1.2 Justification of the Trial Design

There is currently no data on concomitant administration of CYD dengue vaccine with other vaccines in the indicated population aged 9-60 years of age. Based on the current age indication of the dengue vaccine, co-administration with Adacel®, currently used in public sector school-based vaccination programs in subjects aged 9 years and above, is needed and will be incorporated into the post-licensure plan. Therefore, the present CYD66 study will investigate the immunogenicity and safety of the CYD dengue vaccine when it is administered concomitantly or sequentially (at least 28 days apart) with Adacel®. In the Philippines, the CYD dengue vaccine received an indication for use in the 9-45 year-old subjects. In order to generate further data in older subjects, it was decided to also administer the CYD dengue vaccine to 46-60 year-old subjects in the present study.

### 5.1.3 Trial Plan

A schedule of assessments and study vaccinations is provided in the [table of study procedures](#).

All information collected during the study visits must be reported into the source documents. Some of the following information will also be recorded in the electronic case report form (eCRF).

### 5.1.4 Visit Procedures

#### Visit 1 (Day 0): Inclusion, Randomization, and Vaccination

The Investigator or designated study personnel will:

- 1) Give the subject's parent/legally acceptable representative information about the trial, obtain written informed consent (ICF and AF when applicable), and give him/her a signed copy.
- 2) Obtain significant medical history about the subject and history of dengue infection/vaccination.
- 3) Collect demographic data.
- 4) Check concomitant medications and record every reportable medication ongoing at the time of vaccination.
- 5) Check inclusion and exclusion criteria for eligibility.
- 6) Allocate a subject number to the subject.
- 7) Scratch-off the randomization list to obtain the group allocation, and sign it.
- 8) Perform a physical examination
- 9) Record the subject's axillary temperature (Group 2).
- 10) For female subjects of childbearing potentiala, perform a urine pregnancy test (Group 2).

a To be considered of non-childbearing potential, a female must be pre-menarche or post-menopausal for at least 1 year, surgically sterile, or using an effective method of contraception or abstinence from at least 4 weeks prior to vaccination and until at least 4 weeks after vaccination.

- 11) Obtain blood samplea from subjects in Group 2 (see [Section 7.1](#) for detailed instructions regarding the handling of blood samples). Blood is to be taken from the limb opposite to the one that will be used for vaccination.
- 12) Review temporary and definitive contraindications to vaccination.
- 13) Inject Tdap vaccine to subjects from Group 2.
- 14) Keep the subject from Group 2 under observation for 30 minutes, and record any immediate AE in the source document (Group 2).
- 15) Record the date of injection, the site and side of injection and the route of administration, as well as the dose number of the vaccine (Group 2).
- 16) Give the subject or parent/legally acceptable representative of subjects in Group 2 a diary card (DC), a thermometer, and a ruler, and go over the instructions for their use. Subjects from Group 1, who will not be vaccinated at V01, will receive a DC for the collection of SAE only.
- 17) Remind the subject or parent/legally acceptable representative to bring back the DC when they return for Visit 2 at a specified date and time.
- 18) Remind the subject or parent/legally acceptable representative to notify the site in case of an SAE.
- 19) Complete the relevant electronic case report form (eCRF) pages for this visit.

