#### ***Visit 2 (Month 1; 28 [+14] days after Visit 1)***

The Investigator or designated study personnel will:

- 1) Check the information entered into the DC by interviewing the subject/subject's parent (s)/legally acceptable representative(s) and request information concerning any medical event, serious or not, that may have occurred since Visit 1.
- 2) Review the DC pages.
- 3) Recheck inclusion and exclusion criteria for Group 1.
- 4) Perform a physical examination
- 5) Record the subject's axillary temperature.
- 6) Collect information regarding the subject's medication status since the previous visit.
- 7) For female subjects of childbearing potential, perform a urine pregnancy test.
- 8) Obtain blood sample (see [Section 7.1](#) for detailed instructions regarding the handling of blood samples). Blood is to be taken from the limb opposite to the one that will be used for

---

a It is important to note that, if the attempt(s) to collect blood is (are) unsuccessful, the subject should be given the opportunity for another attempt, even on another day. If ultimately a blood sample cannot be obtained, the reason will be recorded in the eCRF. In that case, and if the subject wants to participate in the trial, he/she will be vaccinated.

vaccination for sequential injection (Group 2), or from the limb opposite to the one that will be used for CYD dengue vaccine injection for concomitant injection (Group 1).

- 9) Review temporary and definitive contraindications to vaccination
- 10) Inject the first dose of CYD dengue vaccine to all subjects.
- 11) Inject Tdap vaccine to subjects in Group 1 on the opposite side (the one who did not receive the CYD dengue vaccine).
- 12) Keep the subject under observation for 30 minutes, and record any immediate AE in the source document.
- 13) Record the date of injection(s), the site and side of injection(s) and the route of administration(s), as well as the dose number of the vaccine(s).
- 14) Give the subject or parent/legally acceptable representative a DC (both Groups).
- 15) Remind the subject or parent/legally acceptable representative to bring back the DC when they return for Visit 3 at a specified date and time.
- 16) Complete the relevant eCRF pages for this visit.

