### 5.2.5 Exclusion Criteria

An individual fulfilling *any* of the following criteria is to be excluded from trial enrollment:

- 1) Subject is pregnant, or lactating, or of childbearing potential (to be considered of non-childbearing potential, a female must be pre-menarchea or post-menopausal for at least 1 year, surgically sterile, or using an effective method of contraception or abstinence from at least 4 weeks prior to the first vaccination until at least 4 weeks after the last vaccination)
- 2) Participation at the time of study enrollment (or in the 4 weeks preceding the first trial vaccination) or planned participation during the present trial period in another clinical trial investigating a vaccine, drug, medical device, or medical procedure
- 3) Planned receipt of any vaccine in the 4 weeks following any trial vaccination
- 4) Previous vaccination against dengue disease with the trial CYD dengue vaccine
- 5) Receipt of immune globulins, blood or blood-derived products in the past 3 months, which might interfere with assessment of the immune response
- 6) Known or suspected congenital or acquired immunodeficiency (including HIV infection with impaired immune function); or receipt of immunosuppressive therapy such as anti-cancer chemotherapy or radiation therapy within the preceding 6 months; or long-term systemic corticosteroids therapy (prednisone or equivalent for more than 2 consecutive weeks within the past 3 months)
- 7) A previous severe reaction to pertussis, diphtheria or tetanus vaccine including immediate anaphylaxis, encephalopathy within 7 days or seizure within 3 days of receiving the vaccine

---

a For pre-menarche females, the young female patients will declare by themselves (and/or their parent(s) or other legally acceptable representative) if they have not yet started menstruation. If a young female patient reaches menarche during the study, then she is to be considered as a woman of childbearing potential from that time forward. Examples of effective methods of contraception include oral contraception (pill), intrauterine device, diaphragm or condoms, contraceptive foam or cream, hormonal implants, transdermal patch, or parenteral contraception.

- 8) Known systemic hypersensitivity to any of the vaccine componentsa, or history of a life-threatening reaction to the vaccine used in the trial or to a vaccine containing any of the same substances

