### 5.2.7.2 Definitive Contraindications

Should a subject experience one of the conditions listed below, the Investigator will discontinue vaccination:

- 1) Pregnancy, as indicated by a positive urine test, or lactation
- 2) An anaphylactic or other significant allergic reaction to the previous dose of vaccine
- 3) Individual with acquired immunodeficiency (including HIV infection with impaired immune function); or receipt of immunosuppressive therapy, such as anti-cancer chemotherapy, radiation therapy or systemic corticosteroid therapy (prednisone or equivalent)
- 4) Ongoing clinical AE related to the previous trial vaccination, and in the Investigator's opinion, contraindicating further vaccination
- 5) SAE related to the study vaccine following the previous trial vaccination
- 6) Subject classified as a dengue unexposed subject (seronegative) at baseline

Subjects will not be withdrawn due to contraindication but will be followed up for safety and possibly immunogenicity assessment.

If a subject has been classified as a “dengue unexposed”, she/he will have the possibility to continue participating in the safety follow-up.

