### 5.2.12 Follow-up and Reporting of Pregnancies

Pregnancy is an exclusion criterion for enrollment in this study, but a subject could potentially become pregnant during her participation. In case of pregnancy and if at least one dose of the study vaccine(s) has been administered, the subject will not be discontinued from the trial and will be followed for safety assessment (and may be followed for immunogenicity assessment, if applicable). However, no additional vaccination will be administered.

All pregnancy cases should be reported if they occurred during the study and during the 6 month follow up period. To report the pregnancy case, the Investigator must fill out an electronic Pregnancy Reporting Form in the Electronic Data Capture (EDC) system and inform the Sponsor within 1 month after identifying a pregnancy case.

Study staff must then maintain contact with the subject to obtain information about the outcome—i.e., details about the delivery and the newborn, or about pregnancy termination—and must update the electronic Pregnancy Reporting Form. This information should be provided to the Sponsor within 1 month of delivery. Additional follow-up visits may be performed according to the local regulations.

Pregnancy itself is not considered an AE, but any complications during pregnancy are to be considered as AEs, and in some cases could be considered SAEs. Spontaneous abortions, fetal death, stillbirth, and congenital anomalies reported in the baby are always considered as SAEs, and the information should be provided to the Global Pharmacovigilance (GPV) Department regardless of when the SAE occurs (e.g., even after the end of the trial).

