### 7.1.4 Urine Samples

Pregnancy tests are applicable only for any female subjects of childbearing potential. Urine samples for pregnancy tests at the vaccination visits (V01 [Group 2], V02, V04, and V06) will be taken and analyzed at the trial center.

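### The protocol describes childbearing potential in conflicting ways; applied literally, its written definition leaves no eligible female due a pregnancy test at entry

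*Protocol*

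**What the plan says.** **Who may enter.** Exclusion 1 (Protocol 5.2.5, repeated in the synopsis) excludes a female if "Subject is pregnant, or lactating, or of childbearing potential". It then lists four ways to count as not of childbearing potential: before menarche, at least 1 year after menopause, surgically sterile, "or using an effective method of contraception or abstinence from at least 4 weeks prior to the first vaccination" (continuing until 4 weeks after the last).

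**Who is tested.** Visit 1 step 10 (Protocol 5.1.4) orders the urine test for Group 2 females of childbearing potential. Footnote a is attached to that term and gives the same four routes out, the last two reading "surgically sterile, or using an effective method of contraception or abstinence from at least 4 weeks prior to vaccination". Visit 2 step 7 and Visit 4 step 5 use the term without redefining it, and Visit 6 follows Visit 4. Section 7.1.4 is restrictive: "Pregnancy tests are applicable only for any female subjects of childbearing potential".

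**What points the other way.** Section 5.1.1 says: "All female subjects of childbearing potential will provide urine samples for urine pregnancy test before each injection". The footnote to the pregnancy-test row in the Table of Study Procedures, repeated in SAP Table 3.1, gives a female who has reached menarche as its example of who is tested. The footnote to exclusion 1 says that a girl who reaches menarche on study counts as of childbearing potential from then on. It does not make this depend on contraception.

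**What relies on the test.** Before injection, staff must "Review temporary and definitive contraindications to vaccination". The first definitive contraindication in 5.2.7.2 reads "Pregnancy, as indicated by a positive urine test, or lactation".

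**The concern.** Contraception and abstinence do two jobs in this protocol. As eligibility conditions they make sense: a fertile woman may join if she takes precautions. As part of the definition of childbearing potential they also decide who is tested, and there they remove the women for whom a test is most informative.

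At stake is a safeguard before a live attenuated vaccine. The contraindication review depends on a test result that it does not itself order. Under the literal definition, a menarcheal woman using contraception would reach that review with no result. The protocol does not treat eligibility as settling the matter, since it accepts that "a subject could potentially become pregnant during her participation" (5.2.12). The second half of the contraception condition is also a commitment about future conduct, which staff cannot verify on the day of injection.

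**Working it through.** The plan gives no figure to reproduce, so the check is to compare the eligible group with the tested group under each description of the term.

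**Inputs**
- Eligible females: those not of childbearing potential (exclusion 1).
- Tested females: those of childbearing potential (Visit 1 step 10, Visit 2 step 7, Visit 4 step 5, Section 7.1.4).

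**Description A: footnote a and exclusion 1**
1. An eligible female must meet at least one of the four limbs: pre-menarche, post-menopausal, sterile, or using contraception or abstinent.
2. Each limb makes her not of childbearing potential.
3. Only females of childbearing potential are tested.
4. The two groups are complements, so 0 eligible females are due a test at entry.

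The order of the visit steps fits this. At Visit 1, eligibility is checked at step 5 and the test comes at step 10. At Visit 2, Group 1 eligibility is rechecked at step 3 and the test comes at step 7. The earlier step has already removed everyone the later step would test. After entry, a female joins the tested group only if her status changes, for example at menarche or on stopping contraception.

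**Description B: menarche, as in the procedures-table footnote**
1. A menarcheal woman eligible through the contraception limb has reached menarche.
2. She is therefore in the tested group, and the overlap at entry is not empty.

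**Side by side**

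| Eligible female at entry | Due a test under A | Due a test under B |
|---|---|---|
| Pre-menarche | No | No |
| Menarcheal, on contraception or abstinent | No | Yes |

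The second row is the conflict. The on-study menarche rule adds an anomaly. Read as written, a girl who reaches menarche after entry is tested from then on, with no mention of contraception. An abstinent girl who reached menarche before entry is not tested under A.

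**Exposure**
- Planned test occasions for a menarcheal woman who is neither sterile nor post-menopausal: V02 + V04 + V06 = 3 in Group 1. Adding V01 gives 4 in Group 2.
- V06 was not performed (SAP Table 3.1 footnote). For a woman who received both CYD doses, 3 − 1 = 2 occasions fell due in Group 1 and 4 − 1 = 3 in Group 2.
- CYD injections given (SAP Section 1): 676 + 643 + 0 = 1,319, in both sexes together.

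The documents give no split by sex. The 1,319 is therefore only an outer bound on CYD injections in women, and it is not a count of missed tests.

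**The case against.** The strongest reply is that the intended group is evident. Tests are scheduled at four visits, ordered in the visit steps, and stated in the design section. The footnote on the test row itself points to menarche. Description A makes the entry tests pointless, while B gives every provision some effect. Sites may well have tested all menarcheal females.

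Much of this stands. A reader might infer that no eligible woman was tested, or that women were vaccinated untested. The documents support neither: they show conflicting wording and report nothing about what sites did. Nor can footnote a be treated as the only operative text, because the on-study menarche rule is a rule and not an example.

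The reply does not remove the conflict. The procedures-table footnote is only an illustration. The on-study rule does not cover a woman already menarcheal at entry. Footnote a is worded as a definition and sits on the test step.

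Other points limit the consequence. Pregnancy remains an exclusion and a contraindication. A woman entering through the contraception limb must already have taken precautions for at least 4 weeks. The Visit 1 injection is Tdap, so the live-vaccine argument starts at Visit 2. SAP Section 1 states that CYD dosing did not resume after the hold, so new wording cannot protect anyone in this trial.

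**Conclusion.** The text is wrong as written, at low-to-moderate severity. A safety instruction has two incompatible descriptions of whom it covers, and the one worded as a definition gives an empty tested group at entry. That follows from the definitions and needs no assumption beyond applying them literally. Whether any site did so is unknown.

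No missed test is shown, and the number of women concerned cannot be derived. Immunogenicity endpoints, sample size and the analysis are unaffected. The value of correcting it now lies in the protocol text and in any later protocol that reuses the wording.

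**What to change.** Define the term once, in 5.2.5: a female is of childbearing potential unless she is pre-menarche, at least 1 year post-menopausal, or surgically sterile, and one who reaches menarche on study joins the group from that time. Take contraception and abstinence out of the definition.

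Reword exclusion 1, in 5.2.5 and the synopsis, to exclude a female who is pregnant, lactating, or of childbearing potential without effective contraception or abstinence over the existing window (at least 4 weeks before the first vaccination until at least 4 weeks after the last). Entry eligibility should be unchanged, because the same four limbs still admit a woman.

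Replace footnote a at Visit 1 with a cross-reference to the definition. In 7.1.4, state that every female so defined is tested before each injection, whatever her contraception or abstinence. Align the urine-sampling text in the synopsis, Section 5.1.1, the Visit 2, 4 and 6 steps, and the procedures-table footnote.

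No visit or sample type is added. The cost is some extra urine tests, at sites that would have followed the literal definition, at visits where the test is already scheduled. The wording also needs IEC/IRB approval under Section 5.3, because it affects conduct and subject safety.
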